6.2.2. Drugs That May Have Their Plasma Concentrations Altered by Ibrutinib

In vitro studies indicated that ibrutinib is not a substrate of P-glycoprotein (P-gp), but is a mild inhibitor (with an IC_{50} of 2.15 μ g/mL). Ibrutinib is not expected to have systemic drug-drug interactions with P-gp substrates. However, it cannot be excluded that ibrutinib could inhibit

intestinal P-gp after a therapeutic dose. There is no clinical data available; therefore, to avoid a potential interaction in the GI tract, narrow therapeutic range P-gp substrates such as digoxin, should be taken at least 6 hours before or after ibrutinib.

6.2.3. QT Prolonging Agents

Any medications known to cause QT prolongation should be used with caution; periodic ECG and electrolyte monitoring should be considered.

6.2.4. Antiplatelet Agents and Anticoagulants

Warfarin or vitamin K antagonists should not be administered concomitantly with ibrutinib. In an in vitro platelet function study, inhibitory effects of ibrutinib on collagen-induced platelet aggregation were observed. Supplements such as fish oil and vitamin E preparations should be avoided. Use ibrutinib with caution in subjects requiring other anticoagulants or medications that inhibit platelet function. Bleeding events of any grade, including bruising and petechiae, occurred in subjects treated with ibrutinib. Subjects with congenital bleeding diathesis have not been studied. For guidance on ibrutinib and the use of anticoagulants during procedures/surgeries see Section 6.4.

Subjects requiring the initiation of therapeutic anticoagulation therapy (eg, atrial fibrillation), consider the risks and benefits of continuing ibrutinib treatment. If therapeutic anticoagulation is clinically indicated, treatment with ibrutinib should be held and not be restarted until the subject is clinically stable and has no signs of bleeding. Subjects should be observed closely for signs and symptoms of bleeding. No dose reduction is required when study drug is restarted.

6.3. Prohibited Concomitant Medications

Any chemotherapy, experimental therapy, or radiotherapy are prohibited while the subject is receiving study treatment.

Corticosteroids for the treatment of the underlying disease is prohibited except when required to treat Nivolumab toxicity. Corticosteroids for the treatment of non-cancer related reasons for longer than 14 days and/or at doses >100mg of prednisone or its equivalent are prohibited.

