Exclusion Criteria:	
Concurrent Conditions
 
 • Cytotoxic chemotherapy ≤ 21 days prior to first administration of study treatment and/or monoclonal antibody ≤ 4 weeks prior to first administration of study treatment and/or other RCC-directed systemic therapy ≤ 2 weeks prior to first administration of study treatment • Any known additional malignancy that is progressing or requires active treatment. Exceptions include basal cell carcinoma of the skin, squamous cell carcinoma of the skin, or in situ cervical cancer that has undergone potentially curative therapy. • Concurrent systemic immunosuppressant therapy (eg, cyclosporine A, tacrolimus, etc., or chronic administration of >10mg/day of prednisone) within 28 days of the first dose of study drug. • Vaccinated with live, attenuated vaccines within 4 weeks of first dose of study drug. • Recent infection requiring systemic treatment that was completed ≤ 14 days before the first dose of study drug. • Unresolved toxicities from prior anti-cancer therapy, defined as having not resolved to Common Terminology Criteria for Adverse Event (CTCAE, version 4), grade 0 or 1, or to the levels dictated in the inclusion/exclusion criteria with the exception of alopecia. • Known bleeding disorders (eg, von Willebrand's disease) or hemophilia. • History of stroke or intracranial hemorrhage within 6 months

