4.2. Exclusion Criteria

To be enrolled in the study, potential subjects must meet NONE of the following exclusion criteria:

Concurrent Conditions

1. Cytotoxic chemotherapy \leq 21 days prior to first administration of study treatment and/or monoclonal antibody \leq 4 weeks prior to first administration of study treatment and/or other RCC-directed systemic therapy \leq 2 weeks prior to first administration of study treatment
2. Any known additional malignancy that is progressing or requires active treatment. Exceptions include basal cell carcinoma of the skin, squamous cell carcinoma of the skin, or in situ cervical cancer that has undergone potentially curative therapy.
3. Concurrent systemic immunosuppressant therapy (eg, cyclosporine A, tacrolimus, etc., or chronic administration [>14 days] of >10 mg/day of prednisone) within 28 days of the first dose of study drug.
4. Vaccinated with live, attenuated vaccines within 4 weeks of first dose of study drug.
5. Recent infection requiring systemic treatment that was completed \leq 14 days before the first dose of study drug.
6. Unresolved toxicities from prior anti-cancer therapy, defined as having not resolved to Common Terminology Criteria for Adverse Event (CTCAE, version 4), grade \leq 1, or to the levels dictated in the inclusion/exclusion criteria with the exception of alopecia.
7. Known bleeding disorders (eg, von Willebrand's disease) or hemophilia.
8. History of stroke or intracranial hemorrhage within 6 months prior to enrollment.
9. Known history of human immunodeficiency virus (HIV) or active with hepatitis C virus (HCV) or hepatitis B virus (HBV). *Subjects who are positive for hepatitis B core antibody or hepatitis B surface antigen must have a negative polymerase chain reaction (PCR) result before enrollment. Those who are PCR positive will be excluded.*
10. Any uncontrolled active systemic infection.
11. Major surgery within 4 weeks of first dose of study drug.
12. Any life-threatening illness, known autoimmune disease, medical condition, or organ system dysfunction that, in the investigator's opinion, could compromise the subject's safety or put the study outcomes at undue risk.

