5.3.4. Guidelines for Dosage Modification and Treatment Interruption or Discontinuation

Nivolumab treatment will be given for up to one year.

Patients may temporarily suspend study treatment for up to 42 days from the last dose if they experience toxicity that is considered related to the study drug and requires a dose to be held. If nivolumab is held because of adverse events for >42 days beyond the last dose, then the patient will be discontinued from nivolumab.

If a patient must be tapered off steroids used to treat adverse events, nivolumab may be held for additional time beyond 42 days from the last dose until steroids are discontinued or reduced to prednisone dose (or dose equivalent) ≤ 10 mg/day. The acceptable length of interruption will depend on an agreement between the investigator and the Principal Investigator.

Dose interruptions for reason(s) other than toxicity, such as surgical procedures, may be allowed with Principal Investigator approval. The acceptable length of interruption will depend on agreement between the investigator and the Principal Investigator.

Any toxicities associated or possibly associated with nivolumab treatment should be managed according to standard medical practice. Additional tests, such as autoimmune serology or biopsies, may be used to determine a possible immunogenic etiology.

Patients should be assessed clinically (including review of laboratory values) for toxicity prior to, during, and after each infusion. If unmanageable toxicity due to nivolumab occurs at any time during the study, treatment with nivolumab should be discontinued.

Management of potential immune related AEs are described in the following sections.

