5.3.4.5. Endocrine Toxicity

Immune-mediated hypothyroidism and hyperthyroidism has been associated with the administration of nivolumab. In one trial, Grade 1 or 2 hypothyroidism occurred in 8% (21/268) of patients receiving nivolumab. Grade 1 or 2 hyperthyroidism occurred in 3% (8/268) of patients on nivolumab on that trial, and in 1% (1/102) patients receiving chemotherapy. In another trial, hypothyroidism occurred in 4.3% (5/117) of patients. Hyperthyroidism occurred in 1.7% (2/117) of patients. One patient experienced Grade 2 hyperthyroidism.

Patients with unexplained symptoms such as fatigue, headaches, myalgias, impotence, mental status changes, or constipation should be investigated for the presence of thyroid, pituitary, or adrenal endocrinopathies, as well as for hyponatremia or hyperkalemia. An endocrinologist should be consulted if an endocrinopathy is suspected. TSH and free T4 levels should be obtained to determine if thyroid abnormalities are present. TSH, prolactin, and a morning cortisol level will help to differentiate primary adrenal insufficiency from primary pituitary insufficiency.

Hypothyroidism should be managed according to the guidelines in Table 5.

Table 5 Dose Modification Guidelines for Endocrine Toxicity

Toxicity Grade	Management	Follow-up
Asymptomatic endocrinopathy (e.g hypothyroidism or hyperthyroidism)	
 - Continue nivolumab - If TSH <0.5 xLLN or TSH >2x ULN, or consistently out of range in 2 subsequent measurements, include free T4 at subsequent cycles as clinically indicated - Consider endocrinology consult 	Continue standard monitoring
Symptomatic endocrinopathy – either hypothyroidism or hyperthyroidism	
 - continue nivolumab for hypothyroidism or hyperthyroidism - withhold nivolumab for other endocrinopathies with abnormal lab/pituitary scan - evaluate endocrine function - consider pituitary scan - repeat labs in 1-3 weeks - repeat MRI in 1 month if symptoms persist but normal lab/pituitary scan - consider endocrinology consult 	If improved (with or without hormone replacement)- resume nivolumab Continue standard monitoring Patients with adrenal insufficiency may need to continue steroids with mineralocorticoid component

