6. CONCOMITANT MEDICATIONS/PROCEDURES

6.1. Permitted Concomitant Medications

Supportive medications in accordance with standard practice (such as for emesis, diarrhea, etc.) are permitted. Use of neutrophil growth factors (filgrastim and pegfilgrastim) or red blood cell growth factors (erythropoietin) is permitted per institutional policy and in accordance with the ASCO guidelines (Smith 2006). Transfusions may be given in accordance with institutional policy.

Short courses (≤ 14 days) of steroid treatment for non-cancer related medical reasons (eg, joint inflammation, asthma exacerbation, rash, antiemetic use and infusion reactions) at doses that do not exceed 100mg per day of prednisone or equivalent are permitted.

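### Section 6.3 prohibits, after 14 days and at any dose, the low-dose maintenance or replacement steroid on which Exclusion 3 lets patients enter (minor correction)

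*Combined protocol and SAP*

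**What the plan says.** **At entry.** Exclusion 3 in Section 4.2 bars "Concurrent systemic immunosuppressant therapy (eg, cyclosporine A, tacrolimus, etc., or chronic administration [>14 days] of >10 mg/day of prednisone) within 28 days" before study drug starts. For prednisone, the bar applies only when use is both chronic and above 10 mg/day. The synopsis has the same dose limit without the day count: "chronic administration of >10mg/day of prednisone) within 28 days of the first dose of study drug". Two other exclusions can reach steroid users. Exclusion 6 removes patients whose toxicity from earlier cancer treatment has not settled to grade 1 or below. Exclusion 12 mentions autoimmune disease but turns on the investigator's opinion.

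**On study.** Section 6.1 permits steroids for non-cancer reasons as short courses, up to 14 days and up to 100 mg/day of prednisone or equivalent. Section 6.3 states the prohibition: "Corticosteroids for the treatment of non-cancer related reasons for longer than 14 days and/or at doses >100mg of prednisone or its equivalent are prohibited". The sentence before it carries the only exception in that section: "Corticosteroids for the treatment of the underlying disease is prohibited except when required to treat Nivolumab toxicity".

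**For toxicity.** Section 5.3.4 allows nivolumab to be held while steroids are tapered, until they are stopped or down to 10 mg/day or less of prednisone or equivalent. Table 5, on endocrine toxicity, notes: "Patients with adrenal insufficiency may need to continue steroids with mineralocorticoid component".

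**The concern.** The entry rule and the on-study rule treat the same low-dose steroid differently. A patient who has taken 5 to 10 mg/day of prednisone for a long time for a non-cancer condition passes Exclusion 3. Once on study, the same unchanged treatment falls under the prohibition in 6.3. The protocol gives no instruction to taper or stop, and no exemption.

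A site following the text has two courses. It can take the patient off the steroid, which is a safety concern where the steroid is replacement therapy (a clinical judgement; the documents do not discuss it). Or it can continue the steroid and file a protocol deviation notice, which Section 12.7 requires within 2 days of knowledge. The two planned sites could handle the same patient differently.

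**Working it through.** The plan gives no figure on this point and no arithmetic is needed to establish it. The check sets the rules side by side for steroid taken for a non-cancer reason.

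| Use | Exclusion 3 | 6.1 permission | 6.3 prohibition |
|---|---|---|---|
| Up to 100 mg/day, 14 days or less | Not triggered (not chronic) | Met | Not triggered |
| Above 10 mg/day, more than 14 days | Triggered: excluded | Not met | Triggered |
| 10 mg/day or less, more than 14 days | **Not triggered** | **Not met** | **Triggered** |

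The third row is the problem.

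1. *Does duration alone trigger 6.3?* Yes. The two limbs are joined by and/or, so either is sufficient, and the duration limb has no lower dose limit.
2. *Does it matter when the 14 days start?* Section 6.3 does not say. Counted from the start of the steroid, a long-term user is past the limit on study day 1. Counted from the first study dose, the limit is passed on day 15. The result is the same.
3. *Does 6.1 help?* No. It prohibits nothing itself, but its permission stops at 14 days.
4. *Does another rule remove these patients first?* In part. Exclusion 6 may remove patients who take the steroid for unresolved toxicity of earlier treatment. Exclusion 12 may remove some with autoimmune disease, at the investigator's discretion. Neither reaches, for example, replacement for a cause unrelated to prior therapy.
5. *Does an exception cover them?* In part. Prior nivolumab is allowed (Section 4.1), and the exception in 6.3 is not expressly limited to toxicity arising on study, so replacement for earlier nivolumab toxicity is arguably covered. Section 5.3.4 and Tables 2 to 6 concern management of toxicity during study treatment. None of this covers steroid unrelated to nivolumab that predates entry.
6. *What level does the protocol treat as compatible with nivolumab?* 10 mg/day or less: it is the limit in Exclusion 3 and the level at which nivolumab may resume under 5.3.4 and 5.3.4.2.
7. *What follows for the analysis?* Section 10.4.2 defines the evaluable population by completing a cycle and being evaluable for PFS, with no exclusion for deviations. The 15-of-25 rule in 10.3 and 10.5 is therefore unchanged, and so are its stated one-sided level of 0.034 and 90% power. Only the optional per-protocol analysis excludes for deviations, and only those that may affect outcomes.

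**The case against.** The best defence is that the two rules govern different periods. Exclusion 3 is an entry bar for the 28 days before first dose, while 6.3 governs medication on study. Not being excluded is not the same as being permitted to continue, and a stricter on-study rule is a legitimate choice. Both rules can be met if the patient tapers off or is not enrolled.

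Much of this stands. The rules are not logically incompatible, and the documents do not say which reflects the intent. But Exclusion 3 defines chronic use as more than 14 days, the same duration that 6.3 prohibits. The protocol therefore considered long-term use, let it through at 10 mg/day or less, and then barred it without telling sites how to bring the patient off. For replacement steroid, tapering off is not a satisfactory way to comply.

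Two other parts of the defence also stand. Exclusions 6 and 12 and the nivolumab exception shrink the affected group, and the documents give no evidence of its size.

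A reader might go further and infer that 6.3 also bans long-term inhaled, topical or intra-articular steroid, since it names no route. The documents do not support giving that weight. Exclusion 3 is about systemic therapy, and 6.1 and 6.3 express dose in prednisone equivalents, which is a systemic measure.

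**Conclusion.** The point holds as a minor correction. An eligible patient who stays on low-dose maintenance or replacement steroid, for a reason unrelated to nivolumab, breaches 6.3 through duration alone. No text clearly exempts that patient.

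The documents give no basis for estimating how many patients are affected. It may be none of the 30 planned.

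A reader might infer that such patients must come off study treatment, or that the primary result is at risk. Neither follows. Section 9.2 does not list a prohibited medication as a reason to stop; a significant deviation appears there only as an example under investigator decision. The likelier consequence is a deviation notice. The conclusion that the primary analysis is untouched assumes the patient stays on treatment through the first cycle, which the text allows.

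The safety element applies where the steroid is replacement and a site follows 6.3 to the letter.

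**What to change.** Add to Section 6.3, and mirror in 6.1:

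> The 14-day limit does not apply to stable systemic corticosteroid at 10 mg/day or less of prednisone or equivalent, or to physiological replacement; neither limit applies to corticosteroids for nivolumab toxicity under Section 5.3.4.

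The first clause uses a threshold the protocol already applies. The second is a wording repair: the nivolumab exception now sits in the sentence on underlying disease, not in the one with the limits. Tables 2, 3, 4 and 6 call for tapers of about a month or longer and for doses up to 2 mg/kg/day, which exceeds 100 mg/day in any patient above 100 / 2 = 50 kg.

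If the sponsor does intend the stricter on-study rule, the alternative is to tighten Exclusion 3 to bar chronic systemic steroid at any dose. That removes the mismatch but excludes patients on replacement.

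The cost is one sentence in each section, which can travel with the next amendment (drug supplier review, then IRB, under Section 12.9). The downside is slightly longer low-dose steroid exposure on study. Appendix 3 lists glucocorticoids as CYP3A inducers without a strength grade, but 6.2.1 asks sites to avoid only strong inducers and does not name glucocorticoids, so the exemption does not contradict it. Section 7.1.1.4 already requires concomitant medications to be documented. No visit, data item, sample size or analysis changes.

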6.4. Guidelines for Ibrutinib Management with Surgeries or Procedure

Ibrutinib may increase risk of bleeding with invasive procedures or surgery. The following guidance should be applied to the use of ibrutinib in the perioperative period for subjects who require surgical intervention or an invasive procedure while receiving ibrutinib.

6.4.1. Minor Surgical Procedures

For minor procedures (such as a central line placement, needle biopsy, thoracentesis, or paracentesis) ibrutinib should be held for at least 3 days prior to the procedure and should not be

restarted for at least 3 days after the procedure. For bone marrow biopsies that are performed while the subject is on ibrutinib, it is not necessary to hold ibrutinib for these procedures.

6.4.2. Major Surgical Procedures

For any surgery or invasive procedure requiring sutures or staples for closure, ibrutinib should be held at least 7 days prior to the intervention and should be held at least 7 days after the procedure and restarted at the discretion of the investigator when the surgical site is reasonably healed without serosanguineous drainage or the need for drainage tubes.

6.4.3. Emergency Procedures

For emergency procedures, ibrutinib should be held after the procedure until the surgical site is reasonably healed, for at least 7 days after the urgent surgical procedure.

7. STUDY EVALUATIONS

7.1. Description of Procedures

A cycle has a duration of 28 days throughout this study.

All screening clinical and laboratory assessments must be performed within 28 days of Study Day 1 and prior to the first dose of study treatment.

All study tests and procedures should be evaluated at the study center at which the subject was enrolled.

7.1.1. Assessments

7.1.1.1. Informed Consent Form

The subject must read, understand, and sign the Institutional Review Board/Research Ethics Board/Independent Ethics Committee (IRB/REB/IEC) approved informed consent form (ICF) confirming his or her willingness to participate in this study before any study-specific screening procedures are performed.

Subjects must also grant permission to use protected health information per the Health Insurance Portability and Accountability Act (HIPAA). In addition, subjects must sign all approved ICF amendments per the site IRB/REB/IEC guidelines during the course of the study.

The subject may be enrolled in the study only after signing the ICF and being deemed eligible for entry based on screening procedures and history review.

7.1.1.2. Confirm Eligibility

All necessary screening procedures and evaluations, along with review of medical history, must be performed to document that the subject meets all of the inclusion criteria and none of the exclusion criteria (Section 4). In addition to the review of screening procedures and results, documentation of pathologic confirmation of eligible disease (Section 4) is required for confirmation of eligibility prior to enrollment.

7.1.1.3. Medical History

The subject's complete history through review of medical records and by interview will be collected and recorded. Concurrent medical signs and symptoms during screening and prior to first dose of study treatment must be documented to establish baseline severities. A disease history, including the date of initial diagnosis and a list of all prior anticancer treatments, dates administered, response, and duration of response to these treatments is required to be clearly documented in the subject's medical record.

7.1.1.4. Concomitant Medications

All medications from the signing of ICF through 30 days after the last dose of study drug will be documented in the subject's medical record.

7.1.1.5. Adverse Events

The accepted regulatory definition for an adverse event is provided in Section 11.1. All medical occurrences that meet the adverse event definition will be documented in the source documents from the time of first dose of study treatment until 30 days following the last dose of study drugs. SAEs will be reported to the Pharmacyclics and the study sponsor from the time of first dose of study treatment.

Both serious and non-serious AEs will be recorded in the CRF from the first dose of study drug until 30 days after the last dose of study drug(s).

Additional important requirements for adverse event and serious adverse event reporting are explained in Section 11.

7.1.1.6. Physical Examination

The Screening and End-of-Treatment physical examination will include, at a minimum, the general appearance of the subject, height (screening only) and weight (on Nivolumab dosing days), and examination of the skin, eyes, ears, nose, throat, lungs, heart, abdomen, extremities, musculoskeletal system, nervous system, and lymphatic system.

